16.2.1 Definition of Analysis Population

The "Safety Population" will be comprised of all subjects who provide informed consent and receive at least one vaccination. Subjects in the Safety Population will be analysed as treated.

The "Immunogenicity Population" will be comprised of all subjects who received a vaccination and for whom any follow-up immune monitoring data were recorded. This is the dataset to be used for the primary outcomes.

16.2.2 Handling of Missing Data

No adjustments in the analysis for missing data are planned. However, missing immune monitoring data will be explored and, if significant, appropriate statistical methods may be applied to adjust for missing data.

16.2.3 Analysis of Efficacy Variables

MRD levels and immune responses will be summarized descriptively by treatment group and visit as described above. Time to event variables (e.g. time to relapse) will be analysed using survival analysis techniques (e.g, Kaplan-Meier estimates).

16.2.4 Safety analyses

AEs will be classified as treatment emergent AEs (TEAEs) if they start on or after the first vaccination, through 30 days after the last vaccination. AEs that are present prior to the first vaccination, but their severity or relationship increases after the first vaccination, will also be classified as TEAEs.

TEAEs will be tabulated using MedDRA body system and preferred term. The number and percentage of subjects experiencing at least one TEAE overall and at least one TEAE for a body system and preferred term will be tabulated by toxicity grade (CTCAE) and treatment group. A similar summary will be completed by relationship to study product and treatment group. For the calculations in these tables, each subject's TEAEs will be counted once under the maximum toxicity grade or the strongest recorded causal relationship to study product. A summary will be performed for all serious TEAEs. A listing of SAEs will provide details of the events including severity, relationship to study product, time between onset and last vaccination, number of vaccinations received, and a summary of the event. A summary and listing will also be presented for TEAEs causing treatment discontinuation.

Clinical Laboratory results will be summarized descriptively for each treatment group by visit for the observed value as well as for the change from baseline value. In addition, laboratory shift tables will be provided for all laboratory parameters where low/normal/high or abnormal/normal status can be ascertained. In the event of repeat values, the last non-missing value per study day/time will be used for summarization. Listings of individual laboratory parameters by visit with normal ranges and abnormality assessments will also be completed by subject. Laboratory listings will include the study day, date collected, and observed laboratory values with out-of-range values flagged. Unscheduled visit laboratory results will not be summarized but will be included in patient data listings.

For vital signs, descriptive statistics of observed values will be presented for each scheduled visit by treatment group. Changes from baseline to each scheduled post-baseline visit will be presented. All vital sign data by subject will be presented in a listing. Unscheduled visit vital sign data will not be summarized but will be included in patient data listings.

The number and percentage of discontinuation of vaccination and early study termination due to various reasons will be tabulated by treatment group and overall.

Other safety data (e.g. vaccine administration, physical examination, concomitant medications, ECG) will be listed, and summaries presented if appropriate.

Full details of all summary and analysis will be provided in the statistical analysis plan.

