12.3 DOSE LEVELS

Patients will receive 25E6 DCP-001 cells per vaccination (Group 1; 10 patients) or 50E6 DCP-001 cells (Group 2; 10 patients) per vaccination. Both groups will receive two additional booster vaccination of 10E6 cells.

The first treatment for both dose groups is given at Day 0 (Baseline), the second, third and fourth treatments are given at 2 weekly intervals. A total of 4 treatments will be administered in a 6 week timeframe followed by a booster vaccination at 8 and 12 weeks after the 4th vaccination at week 6. A summary of the treatment schedule is given below:

Groups 1 and 2;

Day 0 1st vaccination with 25E6 or 50E6 cells.

Week 2 2nd vaccination with 25E6 or 50E6 cells.

Week 4 3rd vaccination with 25E6 or 50E6 cells.

Week 6 4th vaccination with 25E6 or 50E6 cells.

Week 14 and 18 booster vaccination with 10E6 cells.

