12.4 ROUTE OF ADMINISTRATION

Intradermal (i.d.) administration of the DCP-001 vaccine will be performed by an experienced and suitably trained nurse or physician. The first vaccine is given at Day 0. Two (25E6) or four (50E6) intradermal injections of 0,5 mL max into the upper left or right leg. The second, third and fourth DCP- 001 vaccinations are given at bi-weekly intervals, in close proximity to the first injections. A booster vaccination will be administered on Day 77 (visit 8) and Day 98 (visit 9).

After each vaccination, patients should be monitored for at least 60 minutes to exclude any immediate reactions to the intradermal administration.

Subjects can choose to alternate the leg the vaccine is administered in, or they can have the vaccine in the same leg throughout the study.

Training on vaccine administration and location of injections will be given to all study site members responsible for vaccine administration prior to the start of the study.

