14 STUDY PROCEDURES

14.1 STUDY PROCEDURES AT EACH VISIT

Patients will be screened for eligibility to participate in the study within 4 weeks prior to the first vaccination.

Visit 1 (Screening Visit)

Screening assessments will include:

- Obtaining of written informed consent prior to any study specific procedure (including screening procedures) being performed
- Verify all inclusion criteria are met and no exclusion criteria are met
- Record demographics
- Complete medical history; including previous therapies for AML
- Perform physical examination assessment. The physical examination of baseline will also include WHO Performance status (ECOG)
- Record vital signs (heart rate, blood pressure and oral body temperature)
- Urine analysis
- Perform study specific haematology and biochemistry (incl. beta hCG blood test in woman with child bearing potential)
- Viral screen (HIV, Hepatitis B and C)
- ECG, X-thorax
- HLA typing
- Record any prior and concomitant medications

All laboratory procedures (including central laboratory) will be described in the Laboratory manual.

Treatment Period; Visit 2 (Baseline Visit)/ day 0

The Baseline Visit will include:

- Physical examination, ECOG and Vital signs
- Perform study specific hematology and biochemistry
- Record any new AEs, SAEs and concomitant medications and/or changes in ongoing AEs, SAEs and ongoing concomitant medications
- Blood sample collection for immunological response (immunomonitoring) before vaccination
- Administration of study medication (DCP-001 vaccination)
- Bone marrow aspirate for MRD analysis (MRD assessment) and biobanking

Treatment Period (Visit 3)/ day 2

- Skin biopsy from 1 out of the 2 or 4 injection sites for evaluation of immunological response in skin biopsy
- Blood sample collection for immunological response
- Record new any AEs, SAEs and concomitant medications and/or changes in ongoing AEs,

SAEs and ongoing concomitant medications

- Day is fixed with the previous visit (Visit 2)

Treatment Period (Visit 4-6)/days 14, 28 and 42

The following assessments will be performed at the indicated visits according to the assessment schedule \pm 3 days.

- Physical examination, ECOG and Vital signs
- Hematology and biochemistry
- Record any AEs, SAEs and concomitant medications and/or changes in ongoing AEs, SAEs and ongoing concomitant medications.
- Administration of study medication (DCP-001 vaccination)

Treatment Period (Visit 7)/ day 44

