- Skin biopsy from 1 out of the 2 or 4 injection sites for evaluation of immunological response in skin biopsy.
- Blood sample collection for immunological response
- Record any AEs, SAEs and concomitant medications and/or changes in ongoing AEs, SAEs and ongoing concomitant medications
- Day is fixed with the previous visit (Visit 6)

Treatment Period (Visit 8)/ day 77

according to the assessment schedule \pm 3 days

- Physical examination, ECOG and Vital signs
- Record any new AEs, SAEs and concomitant medications and/or changes in ongoing AEs, SAEs and ongoing concomitant medications
- Blood sample collection for immunological response

Treatment Period (Visit 9-10)/days 98, 126

according to the assessment schedule \pm 3 days

- Physical examination, ECOG and Vital signs
- Hematology and biochemistry
- Record any new AEs, SAEs and concomitant medications and/or changes in ongoing AEs, SAEs and ongoing concomitant medications.
- Administration of study medication (DCP-001 booster vaccination)
- **Visit 9;** Bone marrow aspirate for MRD analysis (MRD assessment) and biobanking

Treatment Period (Visit 11)/day 128

- Skin biopsy from 1 out of the 2 or 4 injection sites for evaluation of immunological response in skin biopsy
- Blood sample collection for immunological response (immunomonitoring)
- Record any new AEs, SAEs and concomitant medications and/or changes in ongoing AEs, SAEs and ongoing concomitant medications
- Day is fixed with the previous visit (visit 10)

Treatment Period (Visit 12)/day 140

according to the assessment schedule \pm 3 days

- Physical examination, ECOG and Vital signs
- Hematology and biochemistry
- Record any AEs, SAEs and concomitant medications and/or changes in ongoing AEs, SAEs and ongoing concomitant medications.
- Bone marrow aspirate for MRD analysis (MRD assessment) and biobanking
- Blood sample collection for immunological response (immunomonitoring)

Treatment Period (Visit 13)/ day 224

according to the assessment schedule \pm 3 days

- Physical examination, ECOG and Vital signs
- Hematology and biochemistry
- Record any new AEs, SAEs and concomitant medications and/or changes in ongoing AEs, SAEs and ongoing concomitant medications.
- Bone marrow aspirate for MRD analysis (MRD assessment) and biobanking
- Blood sample collection for immunological response

Follow-up visits (14-17)

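### A new adverse event that stops the first booster can fall outside the TEAE window, while the same event in a patient who goes on to the booster counts as a TEAE

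*Protocol*

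**What the plan says.** Protocol section 16.2.4 makes an adverse event treatment-emergent if it begins within a window: AEs qualify "if they start on or after the first vaccination, through 30 days after the last vaccination". An AE already present before the first vaccination also qualifies if its severity or relationship increases afterwards; no end date is written for that clause. The tables by body system, preferred term, grade and relationship are all tables of TEAEs. On stopping, the section says: "A summary and listing will also be presented for TEAEs causing treatment discontinuation". The listing of serious events is not limited to TEAEs. Reasons for stopping vaccination are tabulated separately.

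On dosing, section 14.1 has "Treatment Period (Visit 4-6)/days 14, 28 and 42" for the 2nd to 4th vaccinations. Section 12.3 places the boosters by interval, "booster vaccination at 8 and 12 weeks after the 4th vaccination at week 6", and by week, "Week 14 and 18 booster vaccination with 10E6 cells". Section 14.1 puts the booster visits at "Treatment Period (Visit 9-10)/days 98, 126". The synopsis and Table 1 agree. Section 12.4 does not: "A booster vaccination will be administered on Day 77 (visit 8) and Day 98 (visit 9".

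Section 12.5 lets an adverse event end treatment at the physician's discretion. Section 16.2.4 has no rule for a dose that is withheld because of an adverse event.

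**The concern.** The window is anchored to the last vaccination, which is known only in retrospect. Where the interval between doses exceeds 30 days, the status of an event late in that interval depends on whether the next dose is given, and the event itself may decide that. The patient stays in the Safety Population, which needs only one vaccination (section 16.2.1), so the denominator is unchanged while the event leaves the numerator.

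The loss runs one way: an event mild enough for dosing to continue is counted, and one bad enough to stop dosing is not. The table meant to show events that ended treatment is the one most directly affected. Safety and tolerability is a primary objective (section 9.1.1).

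**Working it through.** **Inputs.** Vaccinations 1 to 4 on Days 0, 14, 28 and 42 (sections 12.3 and 14.1, Table 1). Boosters 8 and 12 weeks after the 4th vaccination (section 12.3). Window length 30 days after the last vaccination (section 16.2.4). Visit tolerance ±3 days (Table 1 footnote 8, section 14.1). Last vaccination is read as the last dose received, boosters included; this fits the term booster vaccination and Table 1 footnote 6, which names the booster alongside the last vaccination.

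**The plan's own days.** 42 + 8 × 7 = 98 and 42 + 12 × 7 = 126. Both match section 14.1 and Table 1.

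**Formula.** Uncovered days for a patient who stops before the next dose = (next planned dose day − 1) − (last dose day + 30), or zero if negative.

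| Last dose | Next planned dose | Gap | Uncovered days |
|---|---|---|---|
| Day 0 | Day 14 | 14 | 0 |
| Day 14 | Day 28 | 14 | 0 |
| Day 28 | Day 42 | 14 | 0 |
| Day 42 | Day 98 | 56 | 97 − 72 = 25 (Days 73-97) |
| Day 98 | Day 126 | 28 | 0 |

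Only the interval before the first booster is affected.

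**The same event in two patients.** Take a new AE starting on Day 80.
- Booster given on Day 98: the window runs to at least 98 + 30 = Day 128 (126 + 30 = Day 156 if both boosters are given). The AE is a TEAE.
- Booster withheld because of the AE: the last dose remains Day 42 and the window ended on 42 + 30 = Day 72. The AE is not a TEAE and cannot enter the discontinuation summary or listing.

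**Visit windows.**
- Shortest: 4th dose Day 45, booster due Day 95. 94 − 75 = 19 days.
- Longest: 4th dose Day 39, booster due Day 101. 100 − 69 = 31 days.

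**Section 12.4 days.** With the first booster on Day 77 the gap is 35 days and the uncovered stretch is 76 − 72 = 4 days (Days 73-76). With the same ±3-day tolerance it ranges from zero (Day 45 to Day 74: 73 − 75 is negative) to 79 − 69 = 10 days (Day 39 to Day 80).

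**Weight of one patient.** With 10 patients per group, one lost patient is 1/10 = 10 percentage points in the discontinuation table or in a single preferred-term row.

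**The case against.** The strongest reply is that nothing is lost from the data. Sections 15.3 and 15.4 require all AEs to be recorded from consent to the end of study, including the action taken with study treatment. The DSMB reviews SAEs promptly and other AEs periodically (section 15.8). The stop appears in the table of reasons, and a serious event appears in the SAE listing with its time since the last vaccination. This stands, and it limits the point to tabulation. It does not remove it: section 16.2.4 specifies no AE summary outside TEAEs, so a non-serious event that stops treatment is reduced to a count of reasons. Table 1 footnote 6 also ends AE reporting 30 days after the last vaccination or booster unless related events are ongoing, which sits uneasily with section 15.3.

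Second, many stopping events would be unaffected. One that began by Day 72 and still blocks the booster is a TEAE, as is worsening of an AE present before the first vaccination. Section 15.6 expects mainly local skin reactions, which would tend to occur close to a dose. Worsening leukaemia is not an AE (section 15.1), and disease progression is a separate reason for stopping (section 12.5). All of this stands; the loss covers new-onset events only.

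Third, boosters might not count as vaccinations. The window would then end on Day 72 for everyone. The asymmetry would go, but the whole booster period would fall outside the TEAE tables.

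Fourth, full analysis details are left to the SAP. But the window and the restriction of the discontinuation table are fixed here, and an SAP that follows the protocol inherits them.

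A reader might also infer that nearly half of the treatment-stopping events in this interval vanish, because 25 of the 55 days between the 4th vaccination and the first booster (25/55 = 45%) are uncovered. That needs onset to be uniform over the interval, which the protocol does not support.

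**Conclusion.** The point holds as a defect in a stated definition. On the schedule shared by the synopsis, Table 1 and sections 12.3 and 14.1, a new-onset AE on Days 73-97 (25 days; 19 to 31 with visit windows) is or is not a TEAE according to whether the booster follows, and drops out of the TEAE and discontinuation tables when it is the cause of stopping. On the section 12.4 days the stretch is Days 73-76. The asymmetry remains at the nominal days of both schedules; its size depends on how the contradiction is settled.

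This assumes that last vaccination means the last dose received, boosters included. The direction of bias is towards good tolerability, but its size cannot be given: the protocol offers no expected number of patients stopped by new events in this interval, and it may be zero in 20. The 10-point weight per patient does not carry over to overall TEAE incidence if that patient already has another TEAE. No inferential analysis is planned (section 16.2), so no test is affected. It would be wrong to infer that these events go unrecorded or that safety oversight fails. The change is still worth making, because it is cheap and concerns a primary objective.

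**What to change.** Add one sentence to section 16.2.4: any adverse event with onset on or after the first vaccination that leads to a planned vaccination being withheld, or to treatment being discontinued, is classified as a TEAE and enters the TEAE and discontinuation tables, whatever the time since the last dose. State there that the last vaccination means the last dose received, boosters included. Reconcile the booster days in section 12.4 with the synopsis, Table 1 and sections 12.3 and 14.1.

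The cost is the added text and a flag in table programming; the action taken with study treatment is already reported under section 15.3. The downside is that a few late, possibly unrelated events will be counted.

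Extending the window to Day 156 for every early stopper is not needed. A patient who stopped after the Day 0 dose would then be counted for 156 days after a single vaccination, and the rule would conflict with Table 1 footnote 6. With the added sentence, new events on Days 73-97 in patients who stop for other reasons would remain outside the window, but there the event does not decide its own classification.

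### Unscheduled laboratory results are kept out of all laboratory summaries, so the shift tables can miss a transient worst value in the 8- and 12-week gaps between scheduled draws

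*Protocol*

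**What the plan says.** Protocol Section 16.2.4 sets four rules for laboratory data.

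- By-visit summaries: "Clinical Laboratory results will be summarized descriptively for each treatment group by visit for the observed value as well as for the change from baseline".
- Shifts: "laboratory shift tables will be provided for all laboratory parameters where low/normal/high or abnormal/normal status can be ascertained".
- Repeats: "In the event of repeat values, the last non-missing value per study day/time will be used for summarization".
- Unscheduled results: "Unscheduled visit laboratory results will not be summarized but will be included in patient data listings".

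The shift categories are low/normal/high or abnormal/normal. Neither a CTCAE-graded laboratory table nor a worst post-baseline table is mentioned. The listings carry normal ranges and flag values outside them.

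Other sections bear on the point. Section 9.1.1 makes safety and tolerability a primary objective. Section 15.1 counts clinically significant laboratory abnormalities as adverse events, whichever visit they come from. Section 16.2.4 tabulates treatment-emergent events at each subject's worst CTCAE grade, for onsets from the first vaccination to 30 days after the last. Section 15.8 has the DSMB review severe laboratory abnormalities promptly. Section 16.2.4 leaves full detail of the analyses to a SAP, which is not at hand.

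**The concern.** A test taken outside the schedule is often prompted by a symptom or an earlier result, so it is a likely place to find a nadir or peak. If such results enter no laboratory table, the shift tables describe only what happened to be present on the scheduled days. That matters most where scheduled draws are far apart.

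The adverse event route covers only part of this. It depends on an investigator's judgement of clinical significance in an open-label trial. Section 15.1 also sets aside abnormalities present before DCP-001 unless they recur after recovery or get worse to a clinically significant degree, and it does not count worsening of the treated disease. In this population that is a practical limit: inclusion criterion 2 admits patients in CRi, whose counts have not fully recovered, and a new cytopenia may be put down to leukaemia.

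At stake is whether the tabulated laboratory safety of each dose group reflects the worst values seen.

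**Working it through.** The plan gives no figure of its own on this point, so the check is of the schedule and of the routes by which a value can reach a table.

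**Scheduled haematology and biochemistry (Table 1 and Section 14.1).** Day 0 is the baseline visit. The later draws fall under "Treatment Period (Visit 4-6)/days 14, 28 and 42", "Treatment Period (Visit 9-10)/days 98, 126", "Treatment Period (Visit 12)/day 140" and the Day 224 visit. The visit headed "Treatment Period (Visit 8)/ day 77" lists examination, ECOG, vital signs, adverse events and immunomonitoring blood, but no haematology or biochemistry. Table 4 agrees: it shows no diagnostic blood at that visit. The draws are therefore on Days 0, 14, 28, 42, 98, 126, 140 and 224.

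**Gaps.** The successive differences are 14, 14, 14, 56, 28, 14 and 84 days. The two long ones are:

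- 98 − 42 = 56 days (8 weeks). With ±3 days at each end, 50 to 62 days.
- 224 − 140 = 84 days (12 weeks). With ±3 days at each end, 78 to 90 days.

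**Treatment-emergent window.** Table 1 and Section 12.3 put the second booster at week 18, Day 126. The window then closes on Day 126 + 30 = 156.

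- The 56-day gap lies wholly inside the window.
- Of the 84-day gap, 156 − 140 = 16 days lie inside (16/84 = 19%), and 84 − 16 = 68 days lie outside (81%).
- If a patient stops after the fourth vaccination on Day 42, the window closes on Day 42 + 30 = 72. Then 98 − 72 = 26 of the 56 days also lie outside.

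Section 12.4 gives Days 77 and 98 for the boosters, which conflicts with Table 1 and Section 12.3. The passages need reconciling. On the Section 12.4 days the window would close on Day 98 + 30 = 128, before the second gap begins.

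**Where an abnormal unscheduled value in a gap is reported.**

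| Situation | Laboratory tables | TEAE tables | Listings |
|---|---|---|---|
| Reported as an AE, onset in window | no | yes, at worst grade | yes |
| Reported as an AE, onset after window | no | no | yes |
| Not reported as an AE | no | no | yes |

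The last two rows are the loss.

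**Direction.** The worst of a set of values can only stay the same or get worse when more values are added. A shift table restricted to scheduled values therefore cannot show more abnormality than one built on all values, and may show less.

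**Illustration (assumption, not from the documents).** Suppose an abnormality lasts L days and its onset is uniform within a gap of G days. The chance that a scheduled draw falls within it is min(1, L/G).

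| L | G = 14 | G = 56 | G = 84 |
|---|---|---|---|
| 7 days | 50% | 12.5% | 8.3% |
| 14 days | 100% | 25% | 16.7% |
| 28 days | 100% | 50% | 33% |

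Scheduled draws alone would thus miss most abnormalities of one or two weeks in the long gaps. The table says nothing about how many will occur.

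**The case against.** The strongest reply is that the quoted rule suits the tables it governs: event-triggered values would distort by-visit means. That is correct, and those means should stay on scheduled values. The rule as worded, however, also covers the shift tables, where the argument has less force.

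A second reply is that worst-grade toxicity is already summarised through the TEAE tables, the listings flag every out-of-range value, and the DSMB sees severe ones. With about 20 patients and a descriptive analysis, someone can read every line. This stands and limits the weight of the point. It does not give a count per dose group for values not reported as adverse events or arising after the window.

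A third reply is that an extra table is a matter for the SAP. Ordinarily so, but here the protocol states a rule, and a SAP that summarised unscheduled values would contradict it.

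Three stronger readings are tempting and not supported:

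- A reader might infer that unscheduled values are lost from all safety summaries. They are not: the exclusion concerns laboratory summaries, and a clinically significant abnormality with onset in the window enters the TEAE tables.
- A reader might infer that a normal retest overwrites an earlier abnormal result in general. The repeat rule works only within the same study day/time, and a repeat may simply follow a faulty sample.
- A reader might take the share of calendar time in the two gaps as the share of toxicity missed, or convert one missed patient into a change in a graded laboratory rate. Time between draws does not count missed events, and the protocol plans no graded laboratory rate. Nor are patients unobserved in the first gap: visits on Days 44 and 77 record adverse events.

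**Conclusion.** The point holds in a limited form. Section 16.2.4 keeps unscheduled results out of every laboratory table, and no haematology or biochemistry is scheduled for 56 days and again for 84 days. A transient worst value in those periods is tabulated only if reported as an adverse event with onset by about Day 156; otherwise it is found only in a flagged listing. The laboratory shift tables therefore lean towards normal. The same-day repeat rule adds a little in the same direction when the last value is the better one.

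The size of the lean cannot be calculated, because the documents give no rate or duration of laboratory abnormalities. It is likely to be modest, given the small sample, the complete listings, the worst-grade TEAE tables and the DSMB review. No test or decision rule depends on these tables.

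The conclusion assumes that the sentence on unscheduled results applies to shift tables as well as to by-visit statistics, which is its natural reading. The Day 156 figure assumes the last booster on Day 126.

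**What to change.** - Keep by-visit descriptive statistics and change from baseline on scheduled values.
- Amend the sentence on unscheduled results in Section 16.2.4 so that it applies to by-visit summaries only. Possible wording: *Unscheduled laboratory results are left out of by-visit summaries; they are included in the worst post-baseline shift table and in the listings.*
- Add one shift table per dose group from baseline to worst post-baseline value, by CTCAE grade where one exists and by low/normal/high otherwise. Use scheduled, unscheduled and repeat results. Take the worst rather than the last of same-day repeats, unless the earlier sample is documented as invalid. Where both directions matter, show the lowest and highest values separately.

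This needs no new visits, samples or patients. The cost is one extra table set and a protocol wording change, and laboratory toxicity rates may look slightly less favourable. If the SAP already plans such a table, only the protocol sentence needs to be aligned with it.
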